8.1.4 Medical History

The participant's medical history will be obtained by interviewing the participant and a review of the participant's available medical records. Any relevant pre-existing conditions, signs and/or symptoms present prior to the study intervention will be recorded in the eCRF.

8.1.5 Physical Examinations

Physical examination will be performed for each participant.

If the investigator determines that the participant's health on the day of study intervention administration temporarily precludes dosing, the visit will be rescheduled. Refer to the Section 5.4 for the list of criteria for temporary delay of study intervention administration. Treatment of any abnormality observed during this examination has to be performed according to local medical practice outside this study or by referral to an appropriate health care provider.

Physical examination at each study visit after the Screening Visit will be performed only if the participant/participant's caregiver(s) indicates during questioning that there might be some underlying pathology(ies) or if deemed necessary by the investigator or delegate.

8.1.6 Medication and Vaccination History

The participant's medication and vaccination history will be obtained by interviewing the participant and review of the participant's available medical records.

Participant's vaccination history for prior 3 years should be collected.

8.1.7 Biological Samples for Screening

A volume of approximately 10 mL whole blood will be collected at the Screening Visit for the following laboratory assessments: Hematology: complete blood count with differential and platelet count; Chemistry/metabolic panel: Sodium, Potassium, Creatinine, Alanine aminotransferase (ALT), Aspartate aminotransferase (AST), Alkaline Phosphatase, total bilirubin, and blood urea nitrogen (BUN). These laboratory assessments will be performed

locally at the site. Participants with laboratory assessment results of FDA toxicity Grade 1 or lower will be considered eligible to participate in the study (Section 10.3).

8.2 Immunogenicity Assessments

Collected biological samples will be used for protocol-mandated research and purposes related to the improvement, development, validation, and quality assurance of the laboratory tests described in this protocol and for transfer of sera samples to BARDA for future use, for those participants who consented their samples be utilized for further research.

Future findings may make it desirable to use the samples acquired in this study for future research not described in this protocol. All participants will be asked to give a specific consent to allow Sponsor or a contracted partner to use the samples for future research.

Future research will be subjected to prior Independent Ethics Committee (IEC)/Institutional Review Board (IRB) approval if required per local legislation.

Information on further investigations and their rationale can be obtained from Sponsor.

Sample testing will be done in accordance with the recorded consent of the individual participant.

If additional testing is performed, the marker priority ranking given in Section 8.2.3 may be changed.

Collected samples will be stored at GSK for a maximum of 20 years. Samples at BARDA may be stored for 20 years and beyond. This storage period begins when the last participant performed the last study visit, unless local rules, regulations or guidelines require different timeframes or procedures, which would then be in line with participant consent. These extra requirements need to be communicated formally, discussed, and agreed to with GSK.

8.2.1 Biological Samples

A volume of 40 mL whole blood will be collected at Visits 1, 3, 5, and 6 to provide approximately 15 mL serum intended to be used for assay development/validation, protocol-mandated research and for transfer of sera samples to BARDA for future use (if consented by participant). The protocol-specified testing will be performed at GSK and/or GSK designated laboratories.

Prior to measurement of the immune response, collected blood samples will be used to enable the development and the validation of the assays used in this study (HI and MN).

8.2.2 Laboratory Assays

Table 4 Laboratory Assays

Test classification	System	Component	Method	Laboratory
Humoral Immunity	Serum	Inhibiting hemagglutination titers (A/Astrakhan/3212/2020-like (H5N8))	HI	GSK or GSK designated Lab**
	Serum (subset*)	Neutralizing titers (A/Astrakhan/3212/2020-like (H5N8))	MN	GSK or GSK designated Lab**

Abbreviations: H5N8=Influenza A/Astrakhan/3212/2020-like; HI=hemagglutination inhibition;

MN=microneutralization.

* Subset for Microneutralization testing will be performed on 50% of the participants, randomly selected and equally distributed across the different subgroups.

** GSK laboratory refers to the Clinical Laboratory Sciences (CLS) in Rixensart, Belgium; Wavre, Belgium. CLS may designate testing to GSK Research laboratories in Rixensart, Belgium; Rockville, USA; Sienna, Italy, or to a contracted external partner laboratory.

Please refer to Section 10.2 for a brief description of the assays performed in the study.

The addresses of clinical laboratories used for sample analysis are provided in a separate document accompanying this study protocol.

GSK clinical laboratories have established a Quality System supported by procedures. The activities of GSK clinical laboratories and GSK designated labs (third parties) are audited regularly for quality assessment by an internal (Sponsor-dependent) but laboratory independent Quality Department.

8.2.3 Immunological Read-Outs

Table 5 Immunological Read-Outs

Blood sampling time point		Subset name	No. participants	Component	Components priority rank
Type of contact and timepoint	Sampling time point				
Visit 1 (Day 1)	Pre-Vacc I	HI	520	Vaccine-homologous (A/Astrakhan/3212/2020-like (H5N8))	1
Visit 1 (Day 1)	Pre-Vacc I	MN	260	Vaccine-homologous Influenza (A/Astrakhan/3212/2020-like (H5N8))	2
Visit 3 (Day 22)	Pre-Vacc II	HI	520	Vaccine-homologous Influenza (A/Astrakhan/3212/2020-like (H5N8))	1
Visit 3 (Day 22)	Pre-Vacc II	MN	260	Vaccine-homologous Influenza (A/Astrakhan/3212/2020-like (H5N8))	2
Visit 5 (Day 43)	Post-Vacc II	HI	520	Vaccine-homologous Influenza (A/Astrakhan/3212/2020-like (H5N8))	1
Visit 5 (Day 43)	Post-Vacc II	MN	260	Vaccine-homologous Influenza (A/Astrakhan/3212/2020-like (H5N8))	2
Visit 6 (6 months post dose 2)	Post-Vacc II	HI	520	Vaccine-homologous Influenza (A/Astrakhan/3212/2020-like (H5N8))	1
Visit 6 (6 months post dose 2)	Post-Vacc II	MN	260	Vaccine-homologous Influenza (A/Astrakhan/3212/2020-like (H5N8))	2

Abbreviations: HI=hemagglutination inhibition; MN=microneutralization; No.=number; vacc=vaccine.

8.2.4 Immunological Correlates of Protection

Although there is no accepted correlate of protection against influenza virus, either seasonal or pandemic, the protective role of antibodies against HA and, to a lesser extent, neuraminidase, is well established and has been demonstrated both in experimentally infected animals and humans.¹⁵

For this reason, the induction of HA-specific antibodies is used as a marker of potential vaccine efficacy and the serum HI assay is used to demonstrate this humoral response. Hemagglutination inhibition titers of 1:40 or greater have been associated with protection from influenza illness in at least 50% of participants in challenge studies and correlate with vaccine effectiveness.^{16,17}

8.3 Pre- and Post- Vaccination Procedures

8.3.1 Check Inclusion and Exclusion Criteria

All inclusion and exclusion criteria will be re-checked as described in Sections [5.1](#) and [5.2](#) before dosing on Visit 1 and Visit 3.

8.3.2 Body Temperature

Body temperature must be assessed prior to study intervention administration and/or blood draw.

If the participant has fever (fever is defined as temperature $\geq 38.0^{\circ}\text{C}$ [100.4°F] regardless of the location of measurement) on the day of vaccination, the vaccination visit will be rescheduled within the allowed interval for this visit ([Table 2](#)).

If the investigator determines that the participant's health on the day of vaccination temporarily precludes vaccination, the visit will be rescheduled.

8.3.3 Pregnancy Testing

Female participants of childbearing potential must perform a urine pregnancy test prior to any study vaccine administration. Pregnancy testing must be performed even if the participant is menstruating at the time of the study visit. The study intervention may only be administered if the pregnancy test is negative.

Refer to the Section [10.6.2](#) for the information on study continuation for participant who becomes pregnant during the study.

8.3.4 Medical History

Changes or updates to participant medical history since Screening Visit will be recorded in eCRF.

8.3.5 Medication and Vaccine History

Changes or updates to participant medical history since Screening Visit will be recorded in eCRF.

8.3.6 Post-Vaccination Observation Period

Participants will undergo a 30-minute observation period immediately following administration of each dose of study vaccine, where they will be assessed by a qualified healthcare professional for any signs of any adverse events.

8.4 Safety Assessments

The investigator and any designees are responsible for detecting, documenting, and reporting events that meet the definition of an AE, SAE, or pIMD. The investigator and any designees remain responsible for following up AEs that are serious, considered related to the study intervention or the study, or that caused the participant to discontinue the study.

8.4.1 Safety Laboratory Assessments

At Visits 2 and 4, a whole blood sample of approximately 6 mL will be drawn from the first 50% of participants of each age/dose group for the following laboratory assessments: Hematology: complete blood count with differential and platelet count; Chemistry/metabolic panel: Sodium, Potassium, ALT, AST, Alkaline Phosphatase, total bilirubin, creatinine, and BUN.

The post-vaccination clinical safety laboratory assessments will be performed by a central laboratory as detailed in the Laboratory Manual. See [Section 10.3](#) for the FDA Toxicity Grading Scale. See [Section 10.4](#) for management of participants with abnormal laboratory values.

8.4.2 Study Holding Rules and Safety Monitoring

8.4.2.1 Internal Safety Review Committee

The study will also include 2 planned iSRC reviews. The iSRC reviews will occur after the safety data for the 7 days post dose 1 of the first 50 participants have been recorded and are available. The second iSRC review will occur after the first 50 participants have completed 7 days post dose 2, and the safety data is available.

Enrollment will be capped to 20 participants per day until the iSRC reviews have been completed. Following iSRC recommendation, the enrollment will be opened with no limitations.

8.4.2.2 Study Holding Rules

Holding rules in [Table 6](#) will be assessed by each investigator on a continuous basis. Meeting any of these holding rules will trigger a hold of vaccination irrespective of number of participants enrolled and/or timing of the event.

Of note, no formal holding rules will be applied for other safety data. However, if available, these data will also be reviewed in order to allow an overall assessment of the benefit/risk ratio of vaccination.

If any investigator becomes aware of a holding rule being met, he/she will suspend vaccination and inform the medical monitor immediately.

Table 6 Study Holding Rules

Holding Rule	Event (per dose and per individual study group)	Number of Participants
1a	Death or any life-threatening SAE that cannot be reasonably attributed to a cause other than vaccination as per investigator or Sponsor assessment	≥1
1b	Any non-life-threatening SAE that cannot be reasonably attributed to a cause other than vaccination as per investigator or Sponsor assessment	≥1

Abbreviations: SAE=serious adverse event.

8.5 Adverse Events, Serious Adverse Events, and Other Safety Reporting

The definitions of AEs and SAEs can be found in Section [10.5](#).

The definitions of unsolicited and solicited events can be found in Section [10.5.1](#).

Adverse events will be reported by the participant (or, when appropriate, by a caregiver, surrogate).

The investigator and any qualified designees are responsible for detecting, documenting, and recording events that meet the definition of an AE or SAE and remain responsible for following up all AEs until the event has resolved, subsided, stabilized, disappeared, or until the event is otherwise explained, or the participant is lost to follow-up, irrespective of seriousness or relatedness (see Section [7.0](#)).

This includes events reported by the participant (or, when appropriate, by a caregiver, surrogate).

The method of recording, evaluating, and assessing causality of AEs and SAEs and the procedures for completing and transmitting SAE reports are provided in Section [10.5](#) and [10.5.3](#).

8.5.1 Time Period and Frequency for Collecting AE, SAE, pIMD, MAE Information

Serious AEs assessed as related to study participation (e.g., study intervention, protocol-mandated procedures, invasive tests, or change in existing therapy) or related to a

GSK product (non-IMP) will be recorded from the time a participant consents to participate in the study.

All SAEs (not related to study participation), pIMDs, medically attended adverse events (MAEs), and pregnancies will be collected from the start of study intervention until 6 months after the last vaccination at the time points specified in the SoA (Section 1.3).

Medical occurrences that begin before the start of study intervention but after obtaining informed consent will be recorded as medical history/current medical conditions, not as AEs.

All SAEs and pIMDs (pIMDs can be serious or non-serious) will be recorded and reported to the Sponsor or designee immediately and under no circumstance should this exceed 24 hours of the investigator's awareness of the event, as indicated in Section 10.5.5. The investigator will submit any updated SAE or pIMD data to the Sponsor or designee within 24 hours of their awareness of the updated information.

All unsolicited AEs that occur within 21 days following administration of each dose of study intervention and MAEs that occur at any time during the study must be recorded onto the appropriate section of the eCRF, irrespective of their intensity or whether or not they are considered related to the study intervention.

All solicited events that occur within 7 days following administration of each dose of study intervention must be recorded into the diary, irrespective of intensity. All other AEs occurring within this time frame should be recorded on the appropriate section of the eCRF, irrespective of their intensity or whether or not they are considered related to the study intervention.

Investigators are not obligated to actively seek information on AEs or SAEs after conclusion of the study participation. However, if the investigator learns of any SAE, including a death, at any time after a participant has been discharged from the study, and he/she considers the event/cause of death to be reasonably related to the study intervention or study participation, the investigator must promptly notify the Sponsor or designee.

The method of recording, evaluating, and assessing causality of AE and SAE and the procedures for completing and transmitting safety reports are provided in Sections 10.5.3 and 10.5.5.

Table 7 Timeframes for Recording and Reporting Safety Information

Event	Screening Visit	Pre-Dose	Visit 1	Visit 2* or Remote Visit	Visit 3	Visit 4* or Remote Visit	Visit 5	Visit 6 6 months post dose 2
			Day 1 Dose 1	Days 8-10	Day 22 Dose 2	Days 29-31	Day 43	
Administration site and Systemic solicited events								
Unsolicited AEs								
AEs/SAEs leading to withdrawal from the study								
SAEs								
SAEs related to the study intervention								
Pregnancy								
All pIMDs								
MAEs								

Abbreviations: AE=adverse event; MAE=medically attended adverse event; SAE=serious adverse event; pIMD=potential immune-mediated disease.

* The first 50% of study participants in each age and dose group will be required to have safety laboratory assessments performed at the clinic 7-days post each vaccination (i.e., Visit 2 and Visit 4). All other participants will have a remote visit with the site.

8.5.2 Method of Detecting AEs and SAEs

Care will be taken not to introduce bias when detecting AEs and/or SAEs. Open-ended and non-leading verbal questioning of the participant is the preferred method to inquire about AE occurrences.

Participants must be made aware of the requirement to report any new medical condition or worsening of any pre-existing medical condition requiring contact with a healthcare professional to the site staff.

8.5.2.1 Clinically Significant Abnormal Laboratory Findings

Post-vaccination clinical laboratory measurements (Section 8.4.1) are scheduled for the first 50% of participants enrolled in each age/dose group. These laboratory measurements may also be performed, and the results obtained as part of critical care or follow-up due to the occurrence of MAEs, SAEs, or pIMDs during the study.

The investigator must review the laboratory report, document that he/she did so, and record any clinically relevant changes occurring during the study in the eCRF. Clinically significant abnormal laboratory findings are those which are associated with an underlying disease judged by the investigator to be more severe than expected for the participant's condition.

These results should be reported as an AE, MAE, SAE, or Adverse Events of Special Interest (AESI) as applicable for the study.

See [Section 10.3](#) for the FDA Toxicity Grading Scale and [Section 10.4](#) for the management of participants with abnormal laboratory values.

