10.5.1 Definition of AE

AE Definition

 An AE is any untoward medical occurrence in a clinical study participant, temporally associated with the use of a study intervention, whether or not considered related to the study intervention. 
NOTE: An AE can therefore be any unfavorable and unintended sign (including an abnormal laboratory finding), symptom, or disease (new or exacerbated) temporally associated with the use of a study intervention.

Definition of Unsolicited AEs, MAEs, and Solicited Events		

 An unsolicited AE is an AE that was not otherwise solicited in a participant diary and that is communicated by a participant/participant's caregiver(s) who has signed the informed consent. Unsolicited AEs include serious and non-serious AEs. An unsolicited AE is an AE that was either not included in the list of solicited events or could be included in the list of solicited events but with an onset outside the specified period of follow-up for solicited events. Unsolicited AEs must have been communicated by [participants/ participant's caregiver(s)] who has signed the informed consent. Unsolicited AEs include both serious and non-serious AEs. Potential unsolicited AEs may be medically attended (i.e., symptoms or illnesses requiring a hospitalization, emergency room visit, or visit to/by a healthcare provider). The participant/participant's caregiver(s) will be instructed to contact the study site as soon as possible to report MAEs, as well as any events that, though not medically attended, are of participant/participant's caregiver(s) concern. Detailed information about reported unsolicited AEs will be collected by qualified study site personnel and documented in the participant's records. Unsolicited AEs that are not medically attended nor perceived as a concern by the participant/participant's caregiver(s) will be collected during an interview with the participant/participant's caregiver(s) and by review of available medical records at the next visit. Solicited events are predefined administration site and systemic events for which the participant is specifically questioned, and which are noted by the participant in their diary. Solicited Administration Site Events 
Table 11 Solicited Administration Site Events
 
 
 All Age Subgroups	
 
 Pain	
 
	All Age Subgroups	Pain
All Age Subgroups		
Pain		

Redness														

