Swelling														
• Solicited Systemic Events														
Table 12 Solicited Systemic Events														

  
 All Age Subgroups	
   
 Fatigue	
 
 Fever	
 
 Headache	
 
 Muscle Ache	
 
 Joint pain	
 
 Shivering (Chills)	
 
 Sweating	
 
 Gastrointestinal symptoms:	
 
  Nausea	
 
  Vomiting	
 
  Diarrhea	
 
  Abdominal pain	
  
		All Age Subgroups	Fatigue	Fever	Headache	Muscle Ache	Joint pain	Shivering (Chills)	Sweating	Gastrointestinal symptoms:	Nausea	Vomiting	Diarrhea	Abdominal pain
All Age Subgroups														
Fatigue														
Fever														
Headache														
Muscle Ache														
Joint pain														
Shivering (Chills)														
Sweating														
Gastrointestinal symptoms:														
Nausea														
Vomiting														
Diarrhea														
Abdominal pain														

Events Meeting the AE Definition

 Any abnormal laboratory test results (hematology, clinical chemistry, or urinalysis) or other safety assessments (e.g., ECG, radiological scans, vital signs measurements), including those that worsen from baseline, considered clinically significant in the medical and scientific judgment of the investigator (i.e., not related to progression of underlying disease). Exacerbation of a chronic or intermittent pre-existing condition including either an increase in frequency and/or intensity of the condition. New condition detected or diagnosed after study intervention administration even though it may have been present before the start of the study. Signs, symptoms, or the clinical sequelae of a suspected intervention-intervention interaction. Signs, symptoms, or the clinical sequelae of a suspected overdose of either study intervention or a concomitant medication. Overdose per se will not be reported as an AE/SAE unless it is an intentional overdose taken with possible suicidal/self-harming intent. Such overdoses should be reported regardless of sequelae.

- Significant failure of an expected pharmacologic or biological action.
- Events that occur as a result of protocol-mandated procedures (i.e., invasive procedures, modification of participant's previous therapeutic regimen).

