Events NOT Meeting the AE Definition

- Any clinically significant abnormal laboratory findings or other abnormal safety assessments that are associated with the underlying disease, unless judged by the investigator to be more severe than expected for the participant's condition.
- The disease/disorder being studied or expected progression, signs, or symptoms of the disease/disorder being studied, unless more severe than expected for the participant's condition.
- Medical or surgical procedure (e.g., endoscopy, appendectomy): the condition that leads to the procedure is the AE.
- An elective surgery/procedure scheduled to occur during a study will not be considered an AE if the surgery/procedure is being performed for a pre-existing condition and the surgery/procedure has been pre-planned prior to study entry. However, if the pre-existing condition deteriorates unexpectedly during the study (e.g., surgery performed earlier than planned), then the deterioration of the condition for which the elective surgery/procedure is being done will be considered an AE.
- Situations in which an untoward medical occurrence did not occur (social and/or convenience admission to a hospital, admission for routine examination.).
- Anticipated day-to-day- fluctuations of pre-existing disease(s) or condition(s) present or detected at the start of the study that do not worsen. Pre-existing diseases will be recorded in the medical history section of the eCRF.
- Hospitalization for elective treatment of a pre-existing condition (known or diagnosed before signing the informed consent) that did not worsen from baseline.

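### Protocol 8.5.2.1 keeps only the exception in the 10.5.1 laboratory rule, so a new, clinically significant abnormality without underlying disease is an AE under one section but not among the results the other tells sites to report

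*Protocol*

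**What the plan says.** Protocol Section 8.5.2.1 covers the post-vaccination safety laboratory tests at Visits 2 and 4, and tests done in the course of care for other events. It has three parts that matter here.

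- A recording duty: the investigator must review the laboratory report and "record any clinically relevant changes occurring during the study in the eCRF".
- A definition: "Clinically significant abnormal laboratory findings are those which are associated with an underlying disease judged by the investigator to be more severe than expected", given that person's health.
- A reporting instruction, directly after the definition: "These results should be reported as an AE, MAE, SAE, or Adverse Events of Special Interest (AESI) as applicable for the study".

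Protocol Section 10.5.1 also deals with laboratory abnormalities, in three places.

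- The general AE definition: "An AE can therefore be any unfavorable and unintended sign (including an abnormal laboratory finding), symptom, or disease (new or exacerbated").
- The list of events that meet the definition includes abnormal laboratory results "considered clinically significant in the medical and scientific judgment of the investigator (i.e., not related to progression of underlying disease").
- The list of events that do not meet it covers clinically significant laboratory results, described as "findings or other abnormal safety assessments that are associated with the underlying disease, unless judged by the investigator to be more severe than expected", given that person's health.

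Section 8.5 opens by pointing to Section 10.5 for these definitions ("The definitions of AEs and SAEs can be found in Section" 10.5). Section 8.5.2.1 itself refers the reader to Section 8.4.1 for the tests, 10.3 for the grading scale and 10.4 for handling of abnormal values. It does not refer to 10.5.1.

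**The concern.** A site deciding whether a Visit 2 or Visit 4 result is an AE would naturally turn to 8.5.2.1, the laboratory-specific instruction. That section ties clinical significance to the presence of an underlying disease. Section 10.5.1 ties it to the absence of a link with disease progression, and lets disease-associated findings in only as an exception.

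The class left out of 8.5.2.1 is the one these draws are best placed to find. Participants must be medically stable (Section 5.1), and a screening laboratory result of Grade 2 or higher is an exclusion (Section 5.2.1, criterion 11). A new abnormality about a week after a dose, with no disease to explain it, is the case most relevant to the vaccine.

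Unsolicited AEs within 21 days of each dose are a primary safety endpoint. AE status also triggers a causality assessment and an outcome assessment (Section 10.5.3.1) and follow-up until the event is resolved or otherwise explained (Section 8.5.4). If sites work from different sections, the same result can receive all of this at one site and none of it at another.

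**Working it through.** The plan states no figure on this point, so the check is a comparison of the two rules. Each is applied to every class of abnormality that the investigator could face.

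**Rule A (Section 8.5.2.1, read literally).** Report if the finding is associated with an underlying disease AND is worse than expected for the participant's condition.

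**Rule B (Section 10.5.1).** It is an AE if the investigator considers it clinically significant and not related to progression of an underlying disease, OR if it is associated with a disease but worse than expected.

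| Class of abnormal result | Rule A (8.5.2.1) | Rule B (10.5.1) | Agree? |
|---|---|---|---|
| (a) No underlying disease involved, judged clinically significant | Not among the results to report | AE | No |
| (b) Associated with an underlying disease, worse than expected | Report | AE | Yes |
| (c) Associated with an underlying disease, not worse than expected | Not among the results to report | Not an AE | Yes |

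The sections conflict in one class of three. Rule A is the second half of Rule B with the first half missing.

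An example of class (a): a participant with normal screening ALT and no liver disease has a Grade 3 ALT at Visit 2, and the investigator judges it clinically significant. Under 10.5.1 it is an AE. Under 8.5.2.1 read literally it fails the first condition, because no underlying disease is involved, so the reporting instruction does not reach it. The recording duty in 8.5.2.1 does reach it, but that duty asks for an entry in the eCRF and does not say the entry is an AE.

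Number of scheduled draws under this wording:

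- Planned enrolment: 520 (Section 4.1).
- Share with safety draws at Visits 2 and 4: the first 50% in each age and dose group (Sections 4.1 and 8.4.1).
- Participants: 0.5 × 520 = 260.
- Scheduled draws: 260 × 2 = 520.

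This is the number of occasions on which the wording applies. It is not a count of AEs missed. The documents give no rate of class (a) abnormalities and no information on which section any site followed.

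**The case against.** There is a fair case that the protocol as a whole is sound and this is only a clumsy sentence.

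- Section 8.5 sends the reader to Section 10.5 for the AE definition, that definition names abnormal laboratory findings, and nothing in 8.5.2.1 claims to override it. This stands, and it answers a stronger reading that a reader might infer: that new abnormalities in people without disease fall outside AE reporting altogether. They do not, because 10.5.1 captures them when they are judged clinically significant. What remains is that the laboratory-specific section does not itself point to 10.5.1.
- A reader might also take the two sections to be opposites. They are not. They give the same answer for both classes of disease-associated finding.
- The laboratory signal is captured without AE coding. An increase in toxicity grade 7 days after each dose is its own primary safety endpoint, analysed for each test and across tests with exact confidence intervals (Protocol 9.4.3.2, SAP 16.2), with a shift table (SAP Section 16) and listings. This stands, and it limits the damage considerably. It does not replace AE status, because a grade-increase percentage carries no causality, outcome or follow-up. Repeat tests at ad-hoc visits are left out of the by-visit summaries and only listed (SAP 6.3).
- The schema in Section 10.4 (Figure 2) is not visible in the text available, so it may say something about recording. That cannot be excluded.
- Adding AEs late would change data already cleaned and locked for the Day 43 analysis, which gives the sponsor treatment-level unblinded summaries (Protocol 9.5). This is a fair caution about any remedial query and shapes the fix below. It is not an argument for leaving the sentence as it is.

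**Conclusion.** The inconsistency is real but narrow. Section 8.5.2.1 omits the main rule of Section 10.5.1, so a new abnormality without underlying disease that the investigator judges clinically significant is an AE under 10.5.1 and is not among the results that 8.5.2.1 tells sites to report.

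The consequence is possible inconsistency between sites in unsolicited-AE reporting, causality assessment and follow-up. It applies to about 520 scheduled draws in about 260 participants, plus any unscheduled tests. How many AEs are involved cannot be derived from the documents, and there is no evidence that any site under-reported. No hypothesis, power figure, sample size or immunogenicity result is affected.

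The conclusion assumes that the reporting instruction in 8.5.2.1 refers to the findings defined in the sentence just before it, which is the natural reading, and that a site may rely on that section alone. I would rate it a correction worth making, below the level of a must-fix.

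**What to change.** Reconcile the sentence in 8.5.2.1 with the protocol's own rule in 10.5.1. Clinically significant findings would then be those that the investigator judges clinically significant and that are either (i) not associated with an underlying disease, or (ii) associated with one but more severe than would be expected in that participant. Add a cross-reference to 10.5.1.

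Optionally, if the final database is not yet locked, list the post-vaccination toxicity-grade increases that have no matching AE record and send them for blinded investigator review under the 10.5.1 rule. Do not add a grade threshold: neither section has one, and SAP version 4.0 removed a Grade 2 threshold from the laboratory output. Document any AE added after the Day 43 analysis as such. This step matters because correcting the text does not change how results already collected were classified.

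The cost is one sentence, one cross-reference and, if the check is done, a small data-management task. The downside is that final unsolicited-AE counts may be slightly higher than those in the Day 43 output, which the report would need to explain.
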